## **Data Sources**

### **Quantitative Researcher- Assisted Surveys and Assessments**

Participants will complete baseline and follow-up assessments with a trained research assistant. The parent receiving HV services with the index child will complete questionnaires assessing demographics, adversity exposure, positive parenting practices, child development, and relevant covariates and potential mediators/moderators.

### **Ecological Momentary Analysis (EMA) Data**

Parents will be asked to complete brief surveys via the mHealth app twice a day at pre-determined times (morning and evening). These surveys will ask parents to provide information about where they are and with whom, their emotional state, recent parent-child interactions, current stressors or challenges, and their child's emotional and behavioral functioning via the mHealth app.

### **App Feasibility and Effectiveness Data**

We will also collect data on parents' perceptions of app feasibility and effectiveness via survey and a focus group selected from a subset of the 50 participants (up to n =30). We will also track app use (e.g., assessment response rates, number of missing assessments, time spent on app, type of OnDemand content viewed) to provide insight into participant compliance and app interaction.

### **Administrative Data**

The Oklahoma State Department of Health (OSDH) will provide access to administrative data housed in their centralized Efforts To Outcomes (ETO) data system in use by all Maternal, Infant, and Early Childhood Home Visiting (MIECHV) contracted agencies (which includes the three SafeCare programs participating in the proposed study). This system stores benchmark outcome data the research team can utilize to examine whether individual characteristics of parents and families (e.g., number of home visits, completion level of the SafeCare curriculum) predict app utilization outcomes.

## **E. Procedures**

### **Recruitment and enrollment**

All participants in the proposed study will be recruited from three home visiting (HV) programs that deliver the SafeCare+ HV model, which includes modules on healthy parent-child interactions and promoting parenting skills in high-risk families. Families who are eligible for SafeCare+ services generally have one of the following risk factors: mental health issues, intimate partner violence, or substance abuse. We plan to recruit existing and new families in these programs and randomly assign them to one of the two counterbalanced intervention arms.

### **Consenting procedures**

All project consents and HIPAA forms will be collected electronically using REDCap regardless of if the assessment occurs in-person or via telehealth services. REDCap has a feature which allows for version control, automatic time and date stamp, and electronic signature (using a fingertip, computer mouse, or stylus on a tablet screen). After the consent and HIPAA forms are signed in REDCap, these documents will automatically be sent to and stored on the OUHSC secure server as .pdf files. An electronic version of this signed consent and HIPAA form can be emailed directly, or if the participant requests, a paper copy will be provided. If a participant requests additional time to discuss the study with family/friends, a paper or electronic copy of the forms will be provided to the participant to review.

### **Quantitative procedures**

**Baseline assessments.** The research assistant will administer all baseline assessment measures in a virtual interview that will take place via zoom or phone (in person interviews in the participant's home may take place if COVID-19 precautions are lifted). The parent receiving HV services with the index child will complete questionnaires assessing demographics, the child's exposure to adversity, positive parenting practices, child development, and relevant covariates and potential mediators/moderators. (See list of measures below).

*Adversity exposures.* Parents will report on their own (PHL ACEs) and their child's (ACEs) adversity exposure. Children's maltreatment exposure will be assessed via the Parent-Child Conflict Tactics Scale52 and the Child Abuse Potential Inventory.

*Positive Parenting Practices.* Positive parenting practices will be assessed via the Alabama Parenting Questionnaire- Parenting Form. Three subscales of relevance to the aims will be scored and assessed: Inconsistent Parenting, Punitive Parenting, and Positive Parenting.

*Child Development.* The Developmental Profiles-4 will be administered to assess child development. This measure covers multiple domains of development including gross and fine motor skills, adaptive behavior, social-emotional functioning, cognitive functioning, problem-solving, and communication skills.

*Covariates.* Relevant covariates and potential mediators and moderators include family demographics, parent mental health (Center for Epidemiological Studies Depression), parent emotional functioning (Self-Expressiveness in the Family Questionnaire, Emotion Reactivity Scale, Difficulties in Emotion Regulation Scale), child emotional functioning (Emotional Regulation Checklist), parent's protective and compensatory experiences (PACEs), and family economic disadvantage (MacArthur Scale).

These measures will be administered in the baseline and follow-up assessments. For the EMA portion of the proposed project at least one measure from each construct will be administered in a condensed, briefer format.

**Ecological momentary analysis (EMA) study.** Parents will receive twice daily parenting tips and strategies throughout the day. These tips will focus on educating parents about positive parenting practices as a way to promote healthy development in

their child via an adapted SafeCare curriculum. Parents will also be asked to complete brief surveys via the mHealth app once a day at a pre-determined evening time. These surveys will ask parents to provide information about where they are and with whom, their emotional state, recent parent-child interactions, current stressors or challenges, and their child's emotional and behavioral functioning. Parents will receive these once daily surveys and the twice daily parenting tips for two weeks. Of note, during the 4-week EMA study, parents will receive either 2 weeks of the mHealth intervention + EMA data collection followed by 2 weeks of only EMA data collection or to receive 2 weeks of only EMA data collection followed by 2 weeks of mHealth intervention + EMA data collection. The order of mHealth intervention and EMA data collection will be counterbalanced across participants to allow for a within-subjects comparison. Assessment responses will be continuously tracked and stored on a university data server. Additionally, a subset (n =30) of parents will be asked to participate in a brief focus group, during which parents will discuss their experiences with the mHealth app.

**Follow-up assessments.** At the end of the EMA study, parents in both groups will be asked to complete a series of measures in the same manner as the baseline assessment. All measures completed at the baseline assessment will also be completed at follow-up. This final assessment will also include an ease of use and satisfaction survey about the overall app experience.

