**A. Specific Aims**

This is an intervention study to provide in-the-moment parenting tips with the goal of educating parents about monitoring and promoting child development, thereby increasing healthy parent-child interactions leading to resiliency in high-risk children. Specifically, in a sample of parents participating in a HV program, we will use a smartphone app (mHealth app) to deliver twice-daily tailored messages with tips on monitoring and promoting child development. Ecological momentary assessments (EMA) of parents' emotions, parenting behaviors, and interactions with their children will also be collected via the mHealth app. Building off our previous work we expect that parents will evidence greater engagement in positive parenting practices on days when they receive the mobile-based parenting tips and strategies relative to on days when they do not receive this content.

We hypothesize that in-the-moment parenting tips delivered around peak times of parent-child interactions (i.e., before work/school, mealtimes, and bedtime) will promote positive parenting practices in a sample of parents at increased risk of adversity exposure. We aim to use EMA methodology to measure both group level differences (i.e., intervention vs. services as usual) and within-person fluctuations in harsh parenting, children's emotional and behavioral functioning, and positive parenting practices. The study will evaluate the following aims and hypotheses:

**Aim 1. Conduct a 2-arm, randomized, controlled crossover trial to examine the feasibility and effectiveness of a mobile-based parenting app with parents participating in HV services.**

Hypothesis 1a. Parents will report high rates of satisfaction and usability. Hypothesis 1b. Parents will evidence greater engagement in positive parenting practices on days when they receive the mobile-based parenting tips and strategies relative to days when they do not receive this content.

Hypothesis 1c. Groups will evidence increases in positive parenting subscale scores after a month of app engagement.

**Aim 2. Utilize EMA data and follow-up assessments to examine the impact of positive parenting practices on the promotion of child development.**

Hypothesis 2a. Hypothesis 2a. Children will demonstrate less challenging and more positive behavioral functioning on days when their parents receive positive parenting tips.

Hypothesis 2b. Groups will evidence increases in developmental scores after a month of app engagement.

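### The only satisfaction and usability rating is apparently taken in a staff-led interview and covers the whole app, so a favourable Hypothesis 1a result is open to courtesy bias and cannot be credited to the tips

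*Combined protocol and SAP*

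**What the plan says.** **What is to be shown.** Specific Aims states: "Hypothesis 1a. Parents will report high rates of satisfaction and usability". The parent aim is to "examine the feasibility and effectiveness of a mobile-based parenting app with parents participating in HV services". Both concern the app; neither singles out the tips.

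**How the rating is taken.** Data Sources says: "Participants will complete baseline and follow-up assessments with a trained research assistant". Under Quantitative procedures, the baseline paragraph says: "The research assistant will administer all baseline assessment measures in a virtual interview that will take place via zoom or phone". The follow-up paragraph says "parents in both groups will be asked to complete a series of measures in the same manner as the baseline assessment", and then adds: "This final assessment will also include an ease of use and satisfaction survey about the overall app experience". No self-completed or anonymous mode is described for this survey.

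**How it is tested.** Data Analysis (section I) reports descriptive statistics for these responses. It then applies one-sample Wilcoxon signed rank tests against values that stand for only a little satisfaction or usability. No numeric value is given. Power Analysis treats Hypothesis 1a as mainly descriptive and gives it no sample size.

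**What else is collected.** App Feasibility and Effectiveness Data says: "We will also collect data on parents' perceptions of app feasibility and effectiveness via survey and a focus group". The focus group takes up to 30 of the 50 parents. The same section provides for logging of app use.

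**The concern.** Two features of the measurement limit what a favourable result can mean.

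**Mode.** A parent asked by study staff for an opinion of the study's own app may answer more kindly than in private. Any such shift runs in the direction of Hypothesis 1a. A one-sample test has no second group in which a shift common to all ratings could cancel, and a low reference point needs little help to be exceeded.

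**Target.** The overall experience is four weeks of EMA surveys with tips in two of them. Section H says the results will inform feasibility and scalability of the intervention. An overall rating alone cannot tell the sponsor whether parents liked the tips, tolerated the surveys, or the reverse.

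Neither the mode nor the item target can be corrected in the analysis once follow-up data are in.

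**Working it through.** **1. Where the rating sits.** Three statements have to be read together:

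| Place | Content |
|---|---|
| Data Sources, researcher-assisted surveys | Baseline and follow-up are both completed with a research assistant |
| Quantitative procedures, baseline | The assistant administers every baseline measure by video or phone |
| Quantitative procedures, follow-up | Same manner as baseline; the app survey is included in this assessment |

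The natural reading is that the assistant administers the app survey too. This is an inference: the sentence that adds the survey does not state its mode.

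**2. The plan's own figure.** There is none for Hypothesis 1a. The sample sizes in Power Analysis (79, 34, 54 and 23) reproduce exactly with a two-sided paired t-test at alpha 0.05 and power 0.80, but they belong to the other hypotheses and do not bear on this point.

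**3. How sensitive the test is to a shift (illustration only).** The documents give neither a courtesy shift nor a rating SD, so both are expressed in assumed SD units. Assumptions: normal scores, true centre exactly at the reference point, two-sided alpha 0.05, and 20,000 simulated trials per cell. The probability of a significant result in the favourable direction is:

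| Assumed shift (SD) | n = 30 | n = 40 | n = 50 |
|---|---|---|---|
| 0 | 2.5% | 2.5% | 2.3% |
| 0.1 | 7.4% | 8.6% | 10.1% |
| 0.2 | 18.4% | 22.6% | 27.3% |
| 0.3 | 34.5% | 44.0% | 53.1% |
| 0.5 | 73.4% | 85.5% | 92.4% |

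A rough check uses the mean. With n = 50 its standard error is 1/√50 = 0.141 SD, so a shift of 0.3 SD is 0.3/0.141 = 2.1 standard errors. That is just past the two-sided critical value of 1.96, which agrees with a rejection rate of about one half.

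If true satisfaction is well above the reference point, the test would be favourable anyway. The shift would then matter for the reported means and medians rather than for significance.

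**4. What the overall rating covers.** Study Design gives 4 weeks of EMA (28 days) and 2 weeks of tips (14 days), so 14/28 = 50% of app days carry no scheduled tips. This count of days does not depend on whether surveys come once or twice daily, on which the document is inconsistent. Order matters as well: parents who receive tips first give the rating about two weeks after the tips end, while the others give it straight after them.

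**The case against.** **The mode is not stated.** The phrase about the same manner attaches to the series of measures repeated from baseline. The app survey is new and comes in a separate sentence, and an assistant being present does not prove that answers are spoken. This stands as a caution, and it is why the point says apparently. If self-completion is intended, the protocol should say so.

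**The bias is unproven.** A reader might infer that the ratings are inflated. No part of the documents shows that, or gives a size. Only the exposure to bias is supported.

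**The rating matches its hypothesis.** A reader might infer that Hypothesis 1a should rest on the tips alone. It should not: the hypothesis and Aim 1 concern the app, so that change would replace the hypothesis. The line between tips and surveys is also not clean, because Information security describes a platform that adapts content to survey answers. What remains is a limit on interpretation.

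**A single blended score is not documented.** The items are not given, and Data Analysis speaks of responses and tests in the plural. Items on specific features may already exist, but the plan does not say so.

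**Other data help.** The focus group can separate opinions of tips and surveys, and logged use is not open to courtesy answers. Both points are right. However, the focus group is itself spoken and is analysed for themes, and Data Analysis gives the usage logs no role or threshold in Hypothesis 1a.

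**Conclusion.** The point holds as a modest weakness in measurement. The sole quantitative rating behind Hypothesis 1a sits, on the natural reading, in a staff-led interview. It is tested without a comparator against a low and unquantified bar. A favourable result is therefore open to courtesy bias whose size the documents do not allow anyone to estimate. The simulated percentages show how sensitive the test is under assumed shifts; they are not evidence that a shift exists.

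Separately, an overall-app rating answers Hypothesis 1a as written but cannot by itself show which component parents valued. The day counts of 28 and 14 describe exposure, not the share of a parent's opinion.

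This is a desirable improvement. It does not invalidate Aim 1, and it does not touch Hypotheses 1b to 2b.

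**What to change.** **In Follow-up assessments:** state that parents complete the satisfaction and ease-of-use survey themselves, through a REDCap link or in the app, at the end of the follow-up session. The assistant neither reads the items out nor sees the answers. Send a reminder if the survey is not completed. Leave the adversity and other sensitive measures interviewer-led, because section H relies on the data collector to respond to distress.

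**In Information security and Minimizing risks:** both sections currently give data collectors access to study survey data. Restrict that access for this form; otherwise a promise to parents that the interviewer cannot see their answers would be untrue.

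**In the survey and Data Analysis:** keep the overall-app rating as the basis of Hypothesis 1a. Add short items on the parenting tips and on the EMA surveys, and report them separately.

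**Cost:** one REDCap form setting, a few more items and two edited access statements. REDCap is already in use, and parents already answer surveys themselves in the app. The downside is possibly slightly lower completion than in an interview, including among weaker readers, since the language criterion does not clearly require reading. If dissatisfied parents are the ones who skip it, that too would favour the app. Completing it within the session and sending a reminder limit this, and the completion rate should be reported. The change has to be made before follow-up data are collected.

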### **Withdrawal criteria**

The participant will be withdrawn from the study at their request, or if the questions in the survey are causing severe emotional distress, she may be involuntarily withdrawn at the discretion of the PI. If they become incarcerated, they will also be withdrawn, but if they are released at a subsequent interview, they may be re-consented and resume the original data collection schedule.

### **Disclosure to participants**

In the instance of clinically relevant research results affecting the health and well-being of the participant/child, participants will be contacted and notified. Published results using study data will be made available upon request to all participants. Identifiers might be removed and the de-identified information may be used for future research without additional informed consent from the subject.

### **Information security**

All survey data are collected using REDCap. REDCap is a secure web application for managing survey data. REDCap allows for live data capture, meaning data are immediately stored on secure University servers. REDCap data may only be accessed by study staff using University encrypted devices. Access to study survey data is provided only to data collectors (so they may keep in contact with survey participants) and to personnel who will use data for analysis and reporting.

All trial data related to the parenting intervention will be collected and monitored via the Insight mHealth Platform. The Insight™ Platform will enable the researcher team to create an innovative mobile application that: 1) identifies proximal and distal antecedents to imminent risk behaviors using self-report surveys (i.e., ecological momentary assessments [EMAs]); and 2) conduct a Just-in-Time Adaptive Intervention (JITAI) that

tailors intervention content in real-time based upon survey responses. Insight™ is utilizes a web-based content management system (CMS) for easy access across multiple browsers, and uses architecture that enables the incorporation of new features. Users of this service log into a web-based CMS and follow step-by-step guidance to create and manage research studies, enroll and monitor study participants, create EMA items, create different types of EMAs (e.g., random, daily, participant-initiated) and create specific assessment rules (e.g., two vs. four random assessments per day). Once study parameters and content have been created in the CMS, researchers transfer their study materials into the smartphone application shell. The customized smartphone application can be made available on the Android app store, and will soon be available on the Apple app store. Data are encrypted within the smartphone application and automatically and securely uploaded into mHealth servers. Encrypted data can be downloaded from the server by users at any time. The PIs will monitor the incoming data from the Insight™ platform on a monthly basis to ensure that the trial is conducted according to the approved protocol.

All paper forms are kept in locked filing cabinets behind a locked door in an office requiring a security badge for entry.

Consents will be collected electronically through REDCap and stored electronically on a secure OUHSC server.

#### **F. Inclusion / Exclusion Criteria**

##### **Inclusion Criteria**

Any new or currently enrolled parent in Oklahoma or Tulsa County in MIECHV-funded SafeCare home visiting programs.

##### **Exclusion Criteria**

Parents residing outside of Oklahoma or Tulsa Counties will not be recruited (although if they move to another county between baseline and follow-up, they may be eligible to complete the follow-up survey at the discretion of the Principal Investigator).

Parents who cannot read/speak English or Spanish at an 8th-grade level or higher will not be recruited.

Parents under age 16 will not be recruited. Parents ages 16-17 meeting other eligibility requirements may be recruited using the assent form with signatures from both of his/her parents.

#### **G. Gender/Minority/Pediatric Inclusion for Research**

Women and minorities will be recruited as a part of this study, including pregnant women. Data collectors are trained on fully explaining the consent with the participant, including emphasizing the voluntary nature of research and reminding them that refusal to participate will not affect services they would otherwise receive.

#### **H. Risks and Benefits**

There is little-to-no risk to participant health, but there is a risk of some emotional distress due to the sensitive nature of some of the measures contained in the survey. The data collector will assure participants that refusal to respond to a particular question (with exception of certain demographic measures) or measure will not make them ineligible to participate. If a participant seems to be reacting negatively to items asked (e.g., questions about their history of trauma or intimate partner violence), the data collector may help the participant skip that specific measure.

There may be some risks to privacy. This is addressed in the following section.

### **Minimizing risks**

To address the risks related to information security, all survey data are collected using REDCap. REDCap is a secure web application for managing survey data. REDCap allows for live data capture, meaning data are immediately stored on secure University servers. REDCap data may only be accessed by study staff using University encrypted devices. Access to study survey data is provided only to data collectors (so they may keep in contact with survey participants) and to personnel who will use data for analysis and reporting.

Data collected via the mHealth app are encrypted within the smartphone application and automatically and securely uploaded into mHealth servers. Encrypted data can be downloaded from the server by users at any time. All paper forms are kept in locked filing cabinets behind a locked door in an office requiring a security badge for entry. Consents will be collected electronically through REDCap and stored electronically on a secure OUHSC server.

